4.1.2 Protocol Deviations

Protocol deviations will be tracked by the study team throughout the conduct of the study. Data will be reviewed prior to un-blinding and closure of the database to ensure all important deviations are captured and categorized. Participants with major protocol deviations (defined below) will be excluded from the PP population.

Major deviations of the protocol procedures identified as liable to influence the efficacy outcomes of the study may include, but will not be necessarily limited to the following:

- Violation of inclusion or exclusion criteria
- Significant non-compliance with assigned treatment
- Use of prohibited treatment or medication before or during the study
- Any other reason identified which may affect the efficacy assessments

The number and percentage of participants with any major protocol deviations will be presented by product group and overall (Table 14.1.2) and listed (Listing 16.2.2.1). Any minor protocol deviations will be listed similarly (Listing 16.2.2.2).

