| Per-Protocol | 
 Participants who have all post-treatment assessment and do not have any major protocol deviations that would affect efficacy assessments. Participants with major protocol deviations will be excluded. Depending on the nature of the major protocol deviation and impact on the efficacy variable (s), subjects will be either completely excluded from PP population or only partially excluded from the PP analyses. This will be determined on a case-by-case basis. | 
 Efficacy |

The primary population for assessment of efficacy will be the mITT Population. A PP analysis will be performed on the primary variable if more than 5 % of the subjects in the mITT Population are excluded from the PP Population.

Participants excluded from any of the analysis populations will be listed ([Listing 16.2.3.1](#)), with the reason for exclusion.

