4.3.1 Study Product Compliance and Exposure

For doses administered at school, study-personnel will supervise and ensure complete consumption of test product.

The descriptive summary of total number of expected amount of product to be consumed, actual amount product consumed by product group and overall for all participants in mITT population (Table 14.2.1.1).

The compliance will be calculated using following formula –

Test product compliance:

Test product compliance = Actual Consumption X 100/Expected Consumption

Where, actual and expected consumption are defined below:

- Expected consumption = (2X 150 mL of drink X number of days* between first and last treatment day in the study)
- Actual consumption = Expected consumption – (xx mL total left over at morning + xx mL left over at evening)]

*up to maximum of 9 months (to be converted in days) (as test product is only administered maximum up to 9 month regardless last visit day in study)

Dietary Counselling Compliance:

The dietary counselling compliance will be calculated using following formulas:

- **Participants:**
 - Compliance with Mandatory dietary counselling= (Number of sessions out of session numbers 1 or 2 attended by participant divided by 2) X 100
 - Compliance with Follow-up sessions dietary counselling= (Number of sessions out of session numbers 3-7 attended by participant divided by 5) X 100
- **Parents/LAR:**
 - Compliance with Mandatory dietary counselling= (Number of sessions out of session numbers 1 or 2 attended by parents/LAR divided by 2) X 100
 - Compliance with Follow-up sessions dietary counselling= (Number of sessions out of session numbers 3-7 attended by parents/LAR divided by 5) X 100

Study product compliance listing ([Listing 16.2.5.1](#)) using enrolled population will be presented at the time of blinded data review process. Noncompliance will be assessed on a participant by participant basis. Those participants with product compliance less than 70% or non-compliant with dietary counselling will be excluded from the PP population. Any participant excluded from PP population will be clearly documented in the population definition document.

Exposure to the study product in days will be calculated as date of last day in the study minus date of first date of study product administration +1 for the test group.

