4.4 Analysis of Efficacy

4.4.1 Primary Efficacy Endpoint

4.4.1.1 Primary Efficacy Endpoint Definition

The primary efficacy variable of the study is the number of ill days over a period of nine months.

The definition of number of illness days is following –

Number of illness days: Number of days a subject is ill because of GI and/or respiratory illnesses as diagnosed by study physician, as per the criteria defined, over the intervention duration. This corresponds to total number of days (symptomatic or asymptomatic) in an episode of illness. Each episode is defined as each incidence of illness followed by at least 3 symptom free days.

In an episode if the first occurrence is due to GI illness and second occurrence is due to respiratory illness with less than 3 symptom free days then the overall episode due to GI and/or respiratory will be counted as one and separately it will be one each for GI and respiratory.

The asymptomatic days (or symptom free) days will be calculated programmatically based on the date mentioned on the Diagnosis Form in the following way –

Asymptomatic day = (Second occurrence start date - First occurrence end date) - 1

If asymptomatic day is less than 3 days then two occurrences of illnesses will be calculated and considered as single episode.

Else if asymptomatic days are greater than or equal to 3 days then two occurrences of illnesses will be calculated and considered as different episodes.

Descriptive statistics (n, mean, SD, SE, median, minimum and maximum) by product group will be provided ([Table 14.2.2.1](#)). Number of ill days due to GI and/or respiratory illnesses will be listed for each subject ([Listing 16.2.6.18](#)).

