Study Population: Enrolled Population (N=xx)

Product Group: Test Group

| Subject Number | Age/Sex/Race [1] | Visit(s) Excluded from PP Population | Deviation Reason |
|----------------|------------------|--------------------------------------|---------------------------------|
| 10001 | 25/f | All | Did not meet Inclusion criteria |
| | | From Visit 3 | Inclusion criteria |
| | | Visit 4 only | Treatment non-compliance |

Test Group: Fortified malt based food + Dietary Counselling; Control Group: Dietary Counselling

[1] Age in years; Sex: F = Female, M = Male; Race: A1 = African American/African Heritage, A2 = American Indian Or Alaskan Native, A3 = Asian-Central/South Asian Heritage, A4 = Asian-East Asian Heritage, A5 = Asian-Japanese Heritage, A6 = Asian-South East Asian Heritage, N = Native Hawaiian Or Other Pacific Islander, W1 = White-Arabic/North African Heritage, W2 = White - White/Caucasian/European Heritage, MT = Multiple

Program: xxxxxx.sas

Source: Filename

Page x of y

Programming Note: This listing is based on details in the population definition document.

Fortified malt based food

204477 Statistical Reporting and Analysis Plan Amendment 1 2 November 2018

Protocol 204477

Program Run Date: DDMMYYYY

Listing 16.2.2.2
Minor Protocol Deviations
Enrolled Population

Study Population: Enrolled Population (N=xx)

Product Group: Test Group

| Subject Number | Age/Sex/Race [1] | Deviation Sequence | Start Date/Time of Deviation | End Date/Time of Deviation | Deviation Description |
|----------------|------------------|--------------------|------------------------------|----------------------------|-----------------------|
| XXXXXX | XX/A1 | 1 | DDMMYYYY:HH:MM | DDMMYYYY:HH:MM | XXXXXX |

Test Group: Fortified malt based food + Dietary Counselling; Control Group: Dietary Counselling

[1] Age in years; Sex: F = Female, M = Male; Race: A1 = African American/African Heritage, A2 = American Indian Or Alaskan Native, A3 = Asian-Central/South Asian Heritage, A4 = Asian-East Asian Heritage, A5 = Asian-Japanese Heritage, A6 = Asian-South East Asian Heritage, N = Native Hawaiian Or Other Pacific Islander, W1 = White-Arabic/North African Heritage, W2 = White - White/Caucasian/European Heritage, MT = Multiple

Program: xxxxx.sas

Source: Filename

Page x of y

Fortified malt based food

204477 Statistical Reporting and Analysis Plan Amendment 1 2 November 2018

Protocol 204477

Program Run Date: DDMMYYYY

Listing 16.2.3.1

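### Partial per-protocol exclusion by visit does not fit a nine-month total of ill days, and it contradicts the SAP's own whole-child exclusion rule

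*SAP*

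**What the plan says.** - **Partial exclusion is allowed.** Under the Per-Protocol entry of SAP 4.1.3, "subjects will be either completely excluded from PP population or only partially excluded from the PP analyses", depending on the deviation and its effect on the efficacy variables, decided case by case.
- **The shells make the unit a visit.** Listing 16.2.2.1 has a column headed "Visit(s) Excluded from PP Population". Its sample rows cover all visits, everything from Visit 3 onward (reason: inclusion criteria), and "Visit 4 only | Treatment non-compliance". Table 14.1.2 likewise separates exclusions at all visits from exclusions at a named visit.
- **Other text describes whole-child exclusion.** SAP 4.1.2: "Participants with major protocol deviations (defined below) will be excluded from the PP population". The PP definition in SAP 4.1.3 admits "Participants who have all post-treatment assessment and do not have any major protocol deviations that would affect efficacy assessments". For non-compliance, SAP 4.3.1 states: "Those participants with product compliance less than 70% or non-compliant with dietary counselling will be excluded from the PP population".
- **Scope of the PP analysis.** SAP 4.1.3: "A PP analysis will be performed on the primary variable if more than 5 % of the subjects in the mITT Population" are left out of the PP set. The population table lists efficacy in general against the PP set, but no PP analysis of any other endpoint is specified.
- **The endpoint.** SAP 4.4.1.1: "The primary efficacy variable of the study is the number of ill days over a period of nine months". It is built from Diagnosis Form dates. The model in SAP 4.4.1.2 has school, product group, gender and baseline IDDS, with no term for time observed. SAP 4.4.3 rules out imputation.

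**The concern.** Excluding a visit makes sense when each visit supplies its own measurement. Here each child supplies one number, a count accumulated over nine months. If part of the period is removed and the rest is summed, the count can only stay the same or fall, so the child appears healthier for having deviated. If the two arms lose different amounts of time, the PP difference moves for a reason unrelated to the product. A PP result that agrees with the mITT result, or exceeds it, would normally be read as support, so the set should not contain an artefact of this kind. Separately, a programmer given 4.1.2, 4.1.3 and the shells cannot tell whether a child with a major deviation is out, in, or in for part of the time.

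**Working it through.** **1. What partial exclusion could mean for this endpoint.** There are three readings.

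- *Sum what is kept.* Removed time contributes no ill days. The total can fall and cannot rise.
- *Set the total to missing.* With no imputation, the child leaves the analysis. This is complete exclusion under another name.
- *Rescale to the time kept.* No section provides for this. SAP 4.4.2 does divide by time for episode frequency (episodes x 30 / days between first and last visit), but nothing similar is given for ill days.

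The SAP does not choose between them. Nor does it say which calendar days belong to a dropped visit. In the Schedule of Events, Visits 3 to 9 are counselling sessions, while illness data come from weekly physician reviews.

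**2. Internal consistency.** SAP 4.1.2 and the compliance rule in 4.3.1 remove the child. The PP definition requires every post-treatment assessment, which a child with visits removed would not have. The partial clause in 4.1.3 departs from all three. Table 14.1.2 also has a row for major deviations that do not lead to PP exclusion, which 4.1.2 does not allow for.

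**3. The plan's own figures (SAP 1.4).** Inputs: means 7.0 and 6.3, SDs 2.65 and 2.51, two-sided 5%, 80% power.

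- Pooled SD = sqrt((2.65² + 2.51²)/2) = 2.581.
- For a difference of 0.7, the normal formula gives 214 per arm and the t-based version 215, which is the stated figure.
- 215 x 1.5 = 322.5, rounded up to 323 per arm (646 in total).
- 323 / 0.70 = 461.4, rounded up to 462 per arm, or 924.

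These reproduce, and nothing here alters them.

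**4. Illustration under the first reading.** Assume no true effect, so both arms average 7.0 days, and ill days spread evenly over time. Let p be the share of an arm's children partially excluded and f the share of follow-up each of them loses:

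bias (test minus control) = -7.0 x (p_test x f_test - p_control x f_control)

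The documents give no value for p or f; all values below are assumptions. Nine months is taken as 39 weeks. Four weeks is the spacing from Visit 4 (week 2) to Visit 5 (week 6). Dropping is in the test arm only.

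| Test children affected | Time lost | Calculation | Bias (days) | Share of 0.7 |
|---|---|---|---|---|
| 5% | 4 of 39 weeks | 7.0 x 0.05 x 4/39 | -0.04 | 5% |
| 10% | one third | 7.0 x 0.10 / 3 | -0.23 | 33% |
| 20% | one third | 7.0 x 0.20 / 3 | -0.47 | 67% |

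The bias reaches the full 0.7 when p x f = 0.7 / 7.0 = 10%. If control children lose time at half the test rate, each figure halves. If both arms lose equally, the bias is zero.

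**5. The 5% trigger.** With 646 children in the mITT set, 5% is 32.3, so 33 exclusions trigger the PP analysis. The SAP does not say whether a partially excluded child counts.

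**The case against.** The strongest reply is that nothing in the SAP says removed visits would be summed as illness-free. With all post-treatment assessments required and no imputation, a child with excluded visits could equally be set to missing. The 4.1.3 wording about effect on the efficacy variables could mean exclusion by variable rather than by visit. The shells are weak evidence, since they carry leftover template content: the sample subject in Listing 16.2.2.1 is aged 25 in a trial of children aged 7 to 10, and Listing 16.2.5.1 bears another protocol number. The PP analysis is also conditional and supportive only.

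Most of this stands, and it limits the point to what can happen rather than what will. It does not rescue the clause. Setting the child to missing leaves partial exclusion with no meaning. Exclusion by variable has nothing to act on when only one variable has a specified PP analysis. Visit-level exclusion could suit the repeated-measures model in SAP 4.4.1.3, but that model is planned for the ITT population.

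A reader might infer that ill days would be lost mainly in the test arm, so that the rule itself pushes the PP estimate towards the product. The documents do not support that. Product deviations can arise only in the test arm, but compliance below 70%, which Protocol 5.5 judges over the whole study, leads to exclusion of the child from the PP population. Counselling non-compliance, eligibility violations, prohibited medication and visit-window deviations can occur in either arm, and Visit 4 in the sample row is a counselling session for both. A tilt remains possible: lesser product deviations are left to case-by-case judgement, and the trial is open label (Protocol 5.9.2). It is not established.

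**Conclusion.** The point holds as a mismatch between rule and endpoint, with a contradiction inside the SAP. For a nine-month count without a time denominator, partial exclusion by visit either can drop ill days or is complete exclusion, and it disagrees with 4.1.2 and with the PP membership definition. The direction and size of any bias cannot be derived from the documents. The illustrative range of -0.04 to -0.47 day rests on assumed shares, evenly spread ill days, simple summing of what is kept, and dropping confined to the test arm; equal dropping gives zero under no true effect. The consequence is confined to a conditional, supportive analysis. It should still be corrected, because the SAP sets no bound on the effect and the correction is nearly free.

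**What to change.** In SAP 4.1.3, delete the partial-exclusion clause and state that, for the nine-month total of ill days, a child is wholly in or wholly out of the PP set. Remove the visit-level rows from Table 14.1.2 and the visit-level entries from Listing 16.2.2.1. Reconcile 4.1.2 with 4.1.3 on whether every major deviation excludes a child or only those judged to affect efficacy, and keep or drop the Table 14.1.2 row for non-excluding major deviations accordingly. Keeping partial exclusion for the laboratory endpoints would serve no purpose, because no PP analysis of them is specified.

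With whole-child membership, every PP child contributes a full nine-month total, the truncation bias is zero, and the count for the 5% trigger is unambiguous. The cost is a short text change and two shell edits. The PP set may be slightly smaller; the sample size does not change.

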4.2 Subject Demographics and Other Baseline Characteristics

Demographic and baseline characteristics summaries will be produced for the Safety, ITT and mITT population.

4.2.1 Demographic Characteristics

Descriptive statistics (number of subjects [n], mean, and median, standard deviation [SD], minimum and maximum) for the continuous variables and frequency (n) and percentages (%) for categorical variables will be provided for demographic variables.

The continuous variable includes age (years), height (cm), weight (kg), BMI and HAZ and categorical variables include gender, race, and HAZ (for ranges:-3 to -2 and -2 to -1).

This data will be summarized descriptively for all participants in Safety (Table 14.1.4.1), ITT (Table 14.1.4.2), mITT (Table 14.1.4.3) and if required on the PP Population (Table 14.1.4.4). Demographic information will be listed (Listing 16.2.4.1) for enrolled population.

No formal statistical analysis will be performed for this data.

4.2.2 General Medical History

Medical history data will be listed (Listing 16.2.4.2) with start date and end date or ongoing at the start of study product. A data listing will also be produced for evaluation of major protocol deviations at the blinded data review stage.

4.2.3 Characteristics of Disease

Not Applicable.

4.3 Treatments (Study Product, Rescue Medication, other Concomitant Therapies, Compliance)

Compliance data will be summarized on the mITT population. Exposure and other medications will be listed on the enrolled population.

4.3.1 Study Product Compliance and Exposure

For doses administered at school, study-personnel will supervise and ensure complete consumption of test product.

The descriptive summary of total number of expected amount of product to be consumed, actual amount product consumed by product group and overall for all participants in mITT population (Table 14.2.1.1).

The compliance will be calculated using following formula –

Test product compliance:

Test product compliance = Actual Consumption X 100/Expected Consumption

Where, actual and expected consumption are defined below:

- Expected consumption = (2X 150 mL of drink X number of days* between first and last treatment day in the study)
- Actual consumption = Expected consumption – (xx mL total left over at morning + xx mL left over at evening)]

*up to maximum of 9 months (to be converted in days) (as test product is only administered maximum up to 9 month regardless last visit day in study)

Dietary Counselling Compliance:

The dietary counselling compliance will be calculated using following formulas:

- **Participants:**
 - Compliance with Mandatory dietary counselling= (Number of sessions out of session numbers 1 or 2 attended by participant divided by 2) X 100
 - Compliance with Follow-up sessions dietary counselling= (Number of sessions out of session numbers 3-7 attended by participant divided by 5) X 100
- **Parents/LAR:**
 - Compliance with Mandatory dietary counselling= (Number of sessions out of session numbers 1 or 2 attended by parents/LAR divided by 2) X 100
 - Compliance with Follow-up sessions dietary counselling= (Number of sessions out of session numbers 3-7 attended by parents/LAR divided by 5) X 100

Study product compliance listing ([Listing 16.2.5.1](#)) using enrolled population will be presented at the time of blinded data review process. Noncompliance will be assessed on a participant by participant basis. Those participants with product compliance less than 70% or non-compliant with dietary counselling will be excluded from the PP population. Any participant excluded from PP population will be clearly documented in the population definition document.

Exposure to the study product in days will be calculated as date of last day in the study minus date of first date of study product administration +1 for the test group.

Exposure to the study product in days will be calculated as date of last day in the study minus date of first date of dietary counselling +1 for the control group.

Exposure data will be listed ([Listing 16.2.5.1](#)) using enrolled population.

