5.2. Dose Schedule

Participants will be administered two doses of the drink (approx 150 mL each) daily for 9 months. To maximise the interval between the two doses, during all school days study staff will make efforts to administer one dose as soon as the participants enter the school and the second dose will be provided just prior to school dismissal. At home, each day one dose will be administered preferably in the morning and the second dose will be administered preferably in evening, by parents/LARs.

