5.5. Product Compliance

For doses administered at school, study-personnel will supervise and ensure complete consumption of test products. Random home visits will be made by site staff to ensure compliance of product consumption at home. Details of daily product consumption (including weekends, school holidays and school absenteeism) will be entered in the CRF.

In the unlikely event that the test product is incompletely consumed (due to accidental spillage, for instance) or not administered, this will also be noted in the CRF along with the product volume that was not consumed (in case of incomplete consumption). In case this happens at home, parents/LAR will need to enter details in the Product Compliance Report (Appendix 4). Site staff will dispense as many blank reports as appropriate for recording details. Each report will be numbered in an ascending order (for each participant) and records should be maintained to track the total number of reports dispensed and collected. Participant will be considered as non-compliant if the participant consumes less than 70% of the total amount of recommended (for the entire study duration) dose.

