[3] Expected consumption = 2X 150 mL of drink X number of days between first and last treatment day in the study

[4] Actual consumption = [Expected consumption - (xx mL total left over at morning + xx mL left over at evening)]

[5] Test product compliance in %= (actual consumption/ expected consumption) X 100

[6] Mandatory sessions compliance by both participants and patents=(Number of sessions out of session numbers 1 or 2 attended by participant/ parents divided by 2) X 100

[7] Compliance with Follow-up sessions dietary counselling= (Number of sessions out of session numbers 3-7 attended by participant and/or parents/LAR divided by 5) X 100

Program: xxxxxx.sas

Source: Filename

Page x of y

Fortified malt based food

204477 Statistical Reporting and Analysis Plan Amendment 1 2 November 2018

Protocol 204477

Program Run Date: DDMMYYYY

Listing 16.2.5.2
 Prior Medications
 Enrolled Population

Study Population: Enrolled Population (N=xx)

Product Group: Test Group

| Subject Number | Age/Sex/Race[1] | Sequence Number | Drug Name [GSK Drug Synonym] | Reason for Medication | Route of Admin. | Dose per Admin. (unit) | Frequency | Start Date (Study Day [2]) | End Date/ Ongoing |
|----------------|-----------------|-----------------|---------------------------------|-----------------------|-----------------|---------------------------|-----------|-------------------------------|-------------------|
| XXXXXX | XX/A6 | 1 | XXXXXX [XXXXXX] | XXXXXX | XXXXXX | XXXXXX (xx) | XXXXXX | DDMMYYYY (XX) | Ongoing |
| XXXXXX | XX/A6 | 1 | XXXXXX [XXXXXX] | XXXXXX | XXXXXX | XXXXXX (xx) | XXXXXX | DDMMYYYY (XX) | DDMMYYYY |

Test Group: Fortified malt based food + Dietary Counselling; Control Group: Dietary Counselling

[1] Age in years; Sex: F = Female, M = Male; Race: A1 = African American/African Heritage, A2 = American Indian Or Alaskan Native, A3 = Asian-Central/South Asian Heritage, A4 = Asian-East Asian Heritage, A5 = Asian-Japanese Heritage, A6 = Asian-South East Asian Heritage, N = Native Hawaiian Or Other Pacific Islander, W1 = White-Arabic/North African Heritage, W2 = White - White/Caucasian/European Heritage, MT=Multiple.

[2] Study day relative to the date of first date of dietary counselling.

Program: xxxxxx.sas

Source: Filename

Page x of y

Programming Note: Similar listing will be generated for Concomitant Medications and Non-Drug Therapies.

Fortified malt based food

204477 Statistical Reporting and Analysis Plan Amendment 1 2 November 2018

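### The SAP measures product compliance only up to the last treatment day, so a child who stops the drink early but completes follow-up can pass the 70% rule that Protocol 5.5 sets against the whole study

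*SAP*

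**What the plan says.** Protocol 5.2 fixes the planned amount: "Participants will be administered two doses of the drink (approx 150 mL each) daily for 9 months". Protocol 5.5 sets the non-compliance rule against that full amount: a child fails who "consumes less than 70% of the total amount of recommended (for the entire study duration) dose".

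SAP 4.3.1 uses a different denominator: "Expected consumption = (2X 150 mL of drink X number of days* between first and last treatment day in the study". Its asterisk adds only an upper limit of nine months, "as test product is only administered maximum up to 9 month regardless last visit day in study". The footnote to Listing 16.2.5.1 gives the formula without the cap: "Expected consumption = 2X 150 mL of drink X number of days between first and last treatment day in the study". Actual consumption is not summed from doses taken. It is expected consumption minus the recorded leftovers ("xx mL total left over at morning + xx mL left over at evening").

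The resulting percentage decides PP membership: "Those participants with product compliance less than 70% or non-compliant with dietary counselling will be excluded from the PP population". SAP 4.1.3 also limits the PP set to "Participants who have all post-treatment assessment and do not have any major protocol deviations that would affect efficacy assessments". Under the same section, the PP analysis of the primary variable is run only if more than 5% of the mITT population is excluded from PP. SAP Section 5, which tabulates departures from the protocol, has no entry on compliance.

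**The concern.** Both documents use 70%, but of different totals. The protocol asks what share of nine months' product the child drank. The SAP asks what share the child drank while still taking it. Days after the last dose enter neither the numerator nor the denominator, so stopping early costs a child nothing in the score.

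Three outputs depend on this percentage. The PP set is meant to show the effect in children who received the product as planned, and it could keep children who received a third of it. Fewer exclusions also make it less likely that the 5% trigger is met, so the PP analysis might not be run at all. Finally, the mean compliance in Table 14.2.1.1 describes the primary analysis population. A reader would use it to judge whether a null result reflects an ineffective product or an under-consumed one.

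**Working it through.** The plan gives no compliance figure to reproduce, so the check applies each formula to the same child.

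**Inputs**
- Daily amount: 2 × 150 = 300 mL (Protocol 5.2, SAP 4.3.1).
- Threshold: below 70% is non-compliant (Protocol 5.5, SAP 4.3.1).
- Planned days, D: neither document converts nine months to days. Assumed D = 270 to 275.
- Last treatment day, s: not defined in the SAP. Taken here as the last dosing day.
- Recorded leftovers up to day s: L mL.

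**Formulas**
- SAP % = 100 × (300s − L) / (300s). With L = 0 this is 100% for every s.
- Protocol % = 100 × (300s − L) / (300D).

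**Results**

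| Child | Stops on day | Consumed (mL) | SAP % | Protocol %, D = 270 | Protocol %, D = 275 |
|---|---|---|---|---|---|
| Finishes every dose | 30 | 9,000 | 100 | 11.1 | 10.9 |
| Finishes every dose | 90 | 27,000 | 100 | 33.3 | 32.7 |
| Finishes every dose | 135 | 40,500 | 100 | 50.0 | 49.1 |
| Finishes every dose | 180 | 54,000 | 100 | 66.7 | 65.5 |
| Drinks 70% of each dose | 90 | 18,900 | 70 | 23.3 | 22.9 |

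The last child scores exactly 70% by the SAP. That is not below 70%, so the rule does not exclude the child.

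**Where the two rules part.** The full planned amount is 300 × 270 = 81,000 mL to 300 × 275 = 82,500 mL. Seventy per cent of that is 56,700 to 57,750 mL. Dividing by 300 gives 189 to 192.5 days, so 189 to 193 whole days of complete dosing. A full-dose child who stops earlier fails the protocol rule and scores 100% by the SAP.

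**The other reading of last treatment day.** Suppose the interval ran to the end of the nine months and every untaken dose counted as leftover. With D = 270, the day-90 child has leftovers of 300 × 180 = 54,000 mL and scores (81,000 − 54,000) / 81,000 = 33.3%, which agrees with the protocol. Both conditions are needed. If the interval ran to the end but untaken doses were not entered as leftovers, the score would be 81,000 / 81,000 = 100% again. The SAP states neither condition.

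**Scale of the trigger.** If the mITT population equalled the 646 planned completers, 5% would be 0.05 × 646 = 32.3, so at least 33 exclusions would be needed before the PP analysis is run.

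**The case against.** The best counter-argument is that the term is undefined and may have been meant differently. The asterisk separates dosing from the last visit, which suggests the authors saw the interval running towards study end. Protocol 5.5 has doses not given noted in the CRF, and Appendix 4 asks parents to report doses missed entirely at home. On that reading the SAP score could match the protocol's. It remains possible, but it is the less natural one. The same SAP section uses a different phrase, the last day in the study, for exposure, and Listing 16.2.1.1 has separate columns for the last product administration and for completion or withdrawal. If the other reading was intended, the SAP still has to say so.

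Four stronger inferences are tempting, and the documents do not support them:

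- *Any child who quits early stays in the PP set.* A child who leaves the study lacks later assessments, so is out of PP under both documents and out of mITT, whatever the compliance score. Only a child who stops the product and keeps attending through Visit 10 is affected.
- *The 70% rule can never remove an early stopper, so PP has no purpose.* Large leftovers before stopping can still bring the score below 70%. PP also still removes eligibility violations, prohibited treatment and counselling non-compliance.
- *Table 14.2.1.1 overstates the volume drunk.* Days after stopping add nothing to the volume. The percentage is what is inflated.
- *The primary result is biased.* The primary analysis is on mITT and does not use compliance.

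Case-by-case review is a real but partial safeguard. SAP 4.1.2 lists significant non-compliance as a possible major deviation, and 4.3.1 has it judged child by child. But 70% is the only numerical criterion for product. Listing 16.2.5.1, which goes to that review, would show a day-90 stopper with 100% compliance beside an exposure that runs to the last day in the study. The clues are a low expected volume there and the last dosing date in another listing.

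**Conclusion.** The point holds for test-group children who stop the product early but complete follow-up. The SAP replaces the protocol's whole-study denominator with one that ends at the last treatment day, and it does not declare the change. On the natural reading (last dosing day), such a child can score up to 100%, and the 70% rule does not exclude that child. With nine months taken as 270 to 275 days, the day-90 case is 100% against about 33%, and misclassification of full-dose children extends to about day 189 to 193.

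The consequences are confined to PP membership, the trigger for the PP analysis, and the reported compliance percentage. Nothing in the documents indicates how many children would stop the product yet stay in follow-up, so the practical effect cannot be sized. The change should still be made, because the rule as written gives the wrong classification and is easily corrected.

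**What to change.** In SAP 4.3.1, the Table 14.2.1.1 footnote and the Listing 16.2.5.1 footnote, define expected consumption for the 70% rule as 2 × 150 mL × the planned nine-month intervention days, and state the number of days used for nine months. Count every dose not taken as zero consumption, including all doses after product is stopped. Children who leave the study need no separate end date: the protocol rule provides none, and they are outside PP in any case.

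If the sponsor prefers to keep an on-product measure, it should define the last treatment day, say how untaken doses count, and declare and justify the departure in SAP Section 5.

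The cost is a one-line change to the formula, using dosing dates already planned for Listing 16.2.1.1. Reported compliance will be somewhat lower if any child stopped early, and more children may be excluded from PP.
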